8.2 Medical History

Medical/surgical, gynecological, menstrual and obstetrical history will be summarized and presented using system organ classes (SOCs) and preferred terms (PTs) from the Medical Dictionary for Regulatory Activities (MedDRA) Version 19.0 or higher for each of the six analysis groups listed in Section 5.3. Subjects reporting more than one medical history within a SOC will be counted only once for that SOC. Subjects reporting more than one medical history for a PT will be counted only once for that PT.

8.3 Prior, Concomitant, and Post-Treatment Medications

Prior, concomitant, and post-treatment medications will be summarized for the full analysis set for subjects who enrolled in the extension study by the six analysis groups listed in Section 5.3.

Prior medications based on data collected prior to the pivotal studies were summarized.

For prior medications administered to treat uterine fibroid symptoms, the following data are collected: dates of administration (including start and stop dates), dose, route, and reason for discontinuation. Prior medications will be summarized for all randomized subjects who received at least one dose of study drug with number and percentage for each analysis group using ATC Classification and preferred terms from the World Health Organization (WHO) Drug Dictionary.

Concomitant medications are those medications, other than study drugs, taken during the treatment period of the extension study with an end date on or after the first dose of study drug or ongoing at the end of study, and a start date prior to or on the last dose of study drug. A medication will be considered a concomitant medication where one of the following three cases occur (1) the start date is missing and the end date is either after or on the first study drug dose date; (2) the start date is prior to or on the last dose of study drug and the end date is missing; (3) both the start date and the end date are missing.

Concomitant medications for all randomized subjects who received at least one dose of study drug will be summarized using ATC Classification and preferred terms from the World Health Organization (WHO) Drug Dictionary with number and percentage for each analysis group.

Other medications taken during the Post-Treatment Follow-up Period of this extension study, which includes all medications with an end date after the last dose of study drug or ongoing at the end of study, will be summarized by ATC Classification and WHO preferred term with number and percentage for each analysis group.

A subject who reports two or more uses of the same medication will be counted only once within each WHO preferred term. A subject with medications with more than one generic name will be counted only once in the overall total. Prior medications, concomitant medications, and other medications during the Post-Treatment Follow-up Period will be summarized separately.

9.0 Subject Disposition

The number of subjects for each of the following categories will be summarized by the six analysis groups listed in Section 5.3:

- All randomized subjects
- Subjects who took at least one dose of study drug
- Subjects who completed the Treatment Period
- Subjects who discontinued from the Treatment Period
- Subjects who completed the Post-Treatment Follow-Up Period
- Subjects who prematurely discontinued from the Post-Treatment Follow-Up Period

Premature discontinuation of the study drug by primary reason and by any reason will be summarized for each of the six analysis groups, with number and percentage and by reason for discontinuation for all subjects who received at least one dose of study drug. Subjects may have multiple reasons for prematurely discontinuing study drug, but will be counted no more than once for the total of "Any Reason."

Premature discontinuation of the study by primary reason and by any reason will be summarized for each of the six analysis groups, with number and percentage and by reason for discontinuation. Subjects may have multiple reasons for prematurely discontinuing during the Post-Treatment Follow-up Period, but will be counted no more than once for the total of "Any Reason."

10.0 Study Drug Exposure

For all subjects who enrolled into the extension study, the duration of study drug exposure in the extension study is defined as the difference between the dates of the first and last doses of the treatment in the extension study plus 1 day. For subjects randomized to active treatment in the pivotal Study M12-815 or Study M12-817, cumulative exposure to study drug in the pivotal studies and the extension study will be the treatment duration of pivotal studies and extension study by taking the sum of the exposure during pivotal studies and the exposure during the extension study. If a subject has a study drug end date in the pivotal study that is after the study drug start day in the extension study, the overlapping days will be only counted once.

Treatment exposure will be summaried for the extension study alone, for the pivotal studies and the extension study, and for the pivotal studies alone, separately. In each summary, the duration (days) of treatment will be summarized with the mean, standard deviation, median, minimum, and maximum for each of the four main analysis groups listed in Section 5.3 and overall. Additionally, the number and percentage of subjects exposed to study drug will be summarized by duration intervals.

In the cumulative summary of the pivotal and extension studies, for subjects randomized to placebo in the pivotal Study M12-815 or Study M12-817, exposure will be summarized only for the treatment duration of extension study. In the summary of exposure in the pivotal studies, for placebo subjects in the pivotal studies, the time on placebo will be summarized.

The duration intervals for the cumulative summary are: 1 - 28 days, > 28 - 56 days, > 56 - 84 days, > 84 - 112 days, > 112 - 140 days, > 140 - 168 days, > 168 - 196 days, > 196 - 224 days, > 224 - 252 days, > 252 - 280 days, > 280 - 308 days, > 308 - 336 days, and > 336 days. The duration intervals for the privotal Studies M12-815 and M12-817 alone, and for the extension Study M12-816 alone are: 1 - 28 days, > 28 - 56 days, > 56 - 84 days, > 84 - 112 days, > 112 - 140 days, > 140 - 168 days, > 168 - 196 days, > 196 - 224 days, > 224 - 252 days.

11.0 Efficacy Analysis

11.1 General Considerations

No statistical tests will be performed.

Unless otherwise specified, categorical data will be summarized by frequency and percentage; descriptive summaries of continuous data will display the mean, SD, median, minimum, and maximum.

For continuous variables, when the analyses of change and/or percent change from Baseline to post-baseline visit(s) are performed, the within-group change from Baseline to each relevant visit will be summarized with the mean, SD, and 95% Confidence Intervals (CIs). At each post-baseline visit, the Baseline mean and post-baseline visit mean will be calculated for all subjects with baseline and post-baseline value at that visit.

Unless otherwise specified, summaries in efficacy analysis will be provided by the four main groups as in Section 5.3.

Information regarding corresponding statistical methods for analyses and any additional statistical measures required for a specific variable/endpoint are provided in the relevant sections.

11.2 Primary Efficacy Analysis

11.2.1 Primary Efficacy Endpoint

The primary endpoint will be the percentage of responders, defined as subjects meeting the following two conditions:

- MBL volume < 80 mL at the Final Month (the last 28 days of treatment), and
- 50% or greater reduction in MBL volume from Baseline to the Final Month (the last 28 days of treatment)

Subjects who prematurely discontinue study drug due to "lack of efficacy," "requires surgery or invasive intervention for treatment of uterine fibroids," or adverse events will be considered as non-responders, regardless if the two conditions above are met or not. Only primary discontinuation reason is considered.

Baseline MBL volume is defined in Section 7.1.

Final Month is defined as in Section 7.2. If a subject has less than or equal to 28 days of treatment, then the Final Month will be the interval between Day 1 to the last dose date.

11.2.2 Primary Analysis of Primary Efficacy Endpoint

The primary analysis of the primary endpoint will be performed using the full analysis set (Section 5.1) in the extension study.

The responder status (yes/no) will be derived from the observed Final Month MBL volume (as in Section 7.6.1.1), using the criteria as described in Section 11.2.1.

For the primary efficacy analysis, the number and proportion of responders meeting the criteria for the primary efficacy endpoint will be summaried by analysis group as observed. The 95% CI using the normal approximation to the binomial distribution will also be provided for the proportion of responders in each analysis group.

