**Primary Efficacy Analysis:**

The primary analysis of the primary endpoint will be performed using the full analysis set, which is comprised of all subjects who took at least one dose of the study drug in this Extension Study.

The alkaline hematin method and the UBQ will be used to assess the MBL volume. The approach of handling missing data will be the same as in the Pivotal Studies.

The percentage of subjects with MBL volume < 80 mL at the Final Month and 50% or greater reduction in MBL volume from baseline to the Final Month in the Extension Study will be summarized by treatment group.

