#### **8.1.7.1.2 Derivation of Primary Efficacy Endpoint**

[figure not shown]
The Final Month MBL volume will be derived as follows:

- If a subject has any evaluable AH data reported during the Final Month (i.e., she has at least 1 day of AH data during the last 28 days of treatment), then her primary endpoint will be based on AH data during the Final Month. The subject's Final Month MBL volume will be the total MBL volume which is the sum of the observed MBL volume over the last 28 days of treatment.

- If a subject is missing the Final Month AH data and the Uterine Bleeding Questionnaire is completed, then:
  - A value of 0 will be assigned to the Final Month MBL volume if no bleeding or spotting, "Subject only had spotting that did not require the use of sanitary products" or "There was no visible blood on the sanitary products" is indicated on the Uterine Bleeding Questionnaire (Appendix D).
- Otherwise, the primary endpoint will be imputed using multiple imputation as described in Section 8.1.7.1.3.

A flow-chart showing how the primary endpoint will be derived is presented in Figure 6.

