**Figure 6. Flow-Chart for Deriving Primary Endpoint**

### **8.1.7.1.3 Multiple Imputation**

The imputation model will include but is not limited to the following variables: baseline MBL volume, treatment group, and 28-day MBL volume at each post-baseline treatment cycle. The final imputation model will be specified in the SAP.

First,  $M$  "semi-complete" datasets will be imputed to produce monotone missing data via MCMC using SAS PROC MI. Then,  $M$  "complete" datasets for the Final Month MBL volume will be generated based on each "semi-complete" dataset via linear regression using SAS PROC MI.  $M$  represents the number of imputed datasets and its value will be specified in the SAP.

Each subject's responder status will be derived based on the imputed Final Month MBL volume from the  $M$  imputed datasets. The percentage of responders will be summarized by treatment group.

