### **8.1.7.1.4 Sensitivity Analysis of the Primary Efficacy Variable**

The sensitivity analyses for the primary endpoint will use different approaches for handling prematurely discontinued subjects and different approaches for dealing with missing Final Month MBL volume. The details of the sensitivity analyses will be specified in the SAP.

Unless otherwise specified, the analysis dataset used for sensitivity analysis is the full analysis set.

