3.0 Introduction

This statistical analysis plan (SAP) describes the planned statistical analyses for elagolix (ABT-620) Study M12-816 titled "Extension Study to Evaluate the Efficacy and Safety of Elagolix in Premenopausal Women with Heavy Menstrual Bleeding Associated with Uterine Fibroids." The analysis plan was created based on the Study Protocol M12-816 Amendment 1 dated 18 December 2017.

This analysis plan describes both the efficacy and safety analyses. The pharmacokinetic data will be analyzed separately and is not addressed in this SAP.

The SAS System 9.2 or above will be used to perform the statistical analyses. No statistical tests will be performed unless otherwise specified.

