7.6.1.1 Observed MBL Volume Over a Window

If there were observed AH data between two study visits (Product Collection Visit or site visit with UBQ completed), then the MBL volume on the days with observed AH data will be the observed AH data and the MBL volume for the rest of days between the two study visits will be imputed as 0 by AH data.

UBQ responses indicate if a subject has any bleeding or spotting since the last study visit (Product Collection Visit or site visit with UBQ completed). If observed evaluable AH data is available over a window, then the UBQ will not be considered.

If the AH data is reported as "NVB" (no visible blood, discarded without assay), "NO BLEED" (no collection due to no bleeding as indicated by subject or clinical site on assay requisition form), or "TL BQL" (total below low limit of quantitation), the numeric value for the AH data will be imputed as 0. If the AH data is reported as other character value ("NULL," "IN ERROR," "NO DATA," and etc.), the corresponding numeric value for the AH data will be set as missing.

The observed MBL volume over a window (such as the Final Month, Month 1 [Study Days 1 – 28], Month 2 [Day 29 – Day 56], Month 3 [Day 57 – Day 84], Month 4 [Day 85 – Day 112], Month 5 [Day 113 – Day 140], and Month 6 [Study Days 141 – 168]) is defined as follows:

- If a subject has any evaluable AH data reported in the window, then the subject's MBL volume in this window will be the total combined observed AH data of validated and non-validated sanitary products over this window.
- If a subject is missing AH data or all AH data are unevaluable in the window and the UBQ is completed and indicates no bleeding or spotting, "Subject only had spotting that did not require the use of sanitary products" or "There was no visible blood on the sanitary products" and covers this window, then:
 - $\circ~$ A value of 0 will be assigned to the MBL volume over this window.
- If a subject is missing AH data or all AH data are unevaluable in the window and the UBQ is completed with no bleeding or spotting or "Subject only had spotting that did not require the use of sanitary products" or "There was no visible blood on the sanitary products" indicated but UBQ does not cover the full window, then:
 - A value of 0 will be assigned to the MBL volume over this window if the days not covered by UBQ response as described above have AH imputed MBL volume (see first paragraph in Section 7.6.1.1) being 0 for those days.

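### SAP 11.2.2 replaces the protocol's multiple imputation of missing Final Month blood loss with an as-observed summary, gives no reason and no denominator, and SAP 11.2.3 omits the promised missing-data sensitivity analysis

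*SAP*

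**What the plan says.** Protocol 8.1.7.1.2 derives Final Month MBL in steps. Evaluable AH data are used if there are any. If there are none, certain UBQ answers give 0 mL. For the rest: "Otherwise, the primary endpoint will be imputed using multiple imputation as described in Section 8.1.7.1.3". Protocol 8.1.7.1.3 then states: "Each subject's responder status will be derived based on the imputed Final Month MBL volume", taken over M imputed datasets. It leaves two details open. The value of M goes to the SAP, and so does the model: "The final imputation model will be specified in the SAP". Protocol 8.1.7.1.4 says the sensitivity analyses will vary the handling of discontinued women and will also use "different approaches for dealing with missing Final Month MBL volume". The protocol synopsis adds: "The approach of handling missing data will be the same as in the Pivotal Studies".

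SAP 3.0 names its source: "The analysis plan was created based on the Study Protocol M12-816 Amendment 1 dated 18 December 2017". SAP 7.6.1.1 applies AH and UBQ zero rules and treats any value still unassigned as missing. SAP 11.2.2 names the full analysis set, takes responder status from the observed Final Month MBL, and says "the number and proportion of responders meeting the criteria for the primary efficacy endpoint will be summaried by analysis group as observed", with a normal-approximation 95% CI. SAP 11.2.3 lists two sensitivity analyses. One ignores the reason for discontinuation and the other uses validated products only.

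**The concern.** Whether to impute was not one of the choices the protocol left to the SAP. Following the SAP therefore gives a primary responder rate that is not the one the protocol defines. The SAP gives no imputation model, no M and no reason for the change. SAP 13.0 lists only changes from SAP version 1.0 and does not mention it.

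Two further gaps follow. The denominator is not written down: the full analysis set points to every dosed woman, while an as-observed summary points to women who have a responder status. And no planned analysis shows how far the result depends on the women without one. The summaries of the two response components in SAP 11.3.1 follow the primary analysis, so they inherit both gaps.

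Efficacy here is descriptive (SAP 11.1). What is at stake is the reported rate and its CI, not a test.

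**Working it through.** **1. The two documents side by side**

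| Step | Protocol | SAP |
|---|---|---|
| Evaluable AH data in the Final Month | Use them (8.1.7.1.2) | Use them (7.6.1.1) |
| No AH data, UBQ indicates none or negligible | 0 mL (8.1.7.1.2) | 0 mL, subject to window coverage (7.6.1.1) |
| Still unresolved | Multiple imputation (8.1.7.1.3) | Missing (7.6.1.1), summarised as observed (11.2.2) |
| Imputation model and M | To be given in the SAP | Not given |
| Sensitivity to missing MBL | Promised (8.1.7.1.4) | None (11.2.3) |

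The protocol text is current. The list of changes in its Appendix M shows that Amendment 1 edited the multiple imputation section, replacing a logistic regression with a summary by group and keeping the imputation.

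**2. Who is affected**

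A woman is affected only if she has no evaluable AH value in the Final Month and no zero from the UBQ or AH rules.

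- She may have bled but discarded or not collected products (UBQ responses in SAP Appendix F). Protocol 8.1.7.1.1 names women who return nothing and report bleeding as a group to be imputed.
- She may have a UBQ with no bleeding "indicated but UBQ does not cover the full window", but only if the uncovered days also lack an AH-imputed zero.
- All her AH results in the window may be unevaluable, with no usable UBQ.
- She may have no post-baseline AH or UBQ data at all. The full analysis set requires only one dose.

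In the primary analysis, women whose primary reason for stopping was an adverse event, lack of efficacy or surgery are non-responders whatever their MBL (SAP 11.2.1), so they are not affected. In the first 11.2.3 analysis that rule is switched off. A woman in this category with no MBL then has no status, and the text does not say how she is handled.

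**3. The denominator**

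The explicit rule that excludes women missing an evaluation is in SAP 12.1 and covers safety only. The efficacy rule in SAP 11.1 concerns means of continuous variables. Neither settles the responder rate.

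**4. Size**

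The plan has no figure to reproduce: it gives no missing rate and no precision target, and about 400 women (protocol 8.2) is an enrolment estimate. Inputs:

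- p_obs, the response rate among women with a status: 79% (standard-dose add-back) and 91.9% (elagolix alone), the Phase 2b rates under protocol 3.2.2.1, used as stand-ins;
- m, the share missing: assumed, 5% and 10%;
- r, the response rate among the missing: unknown, 0 to 1.

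Full-set rate = (1 - m) x p_obs + m x r, so as-observed minus full-set rate = m x (p_obs - r).

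| p_obs | m | r = 0 | r = 1 |
|---|---|---|---|
| 79% | 5% | 0.05 x 0.79 = +3.95 points | 0.05 x (0.79 - 1) = -1.05 |
| 79% | 10% | 0.10 x 0.79 = +7.9 | 0.10 x (0.79 - 1) = -2.1 |
| 91.9% | 5% | 0.05 x 0.919 = +4.6 | 0.05 x (0.919 - 1) = -0.4 |
| 91.9% | 10% | 0.10 x 0.919 = +9.2 | 0.10 x (0.919 - 1) = -0.8 |

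The sign changes at r = p_obs.

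For scale, take an assumed group of 100 with 10 missing. The SAP's CI half-width on the as-observed rate is 1.96 x sqrt(0.79 x 0.21 / 90) = 8.4 points at 79%, and 1.96 x sqrt(0.919 x 0.081 / 90) = 5.6 points at 91.9%. What multiple imputation would give cannot be computed from the documents.

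**The case against.** **The affected group may be small.** The Final Month is the last 28 days up to the last dose (SAP 7.2) and shortens for women treated 28 days or less (SAP 11.2.1), so stopping early does not by itself create a missing value. The zero rules resolve many others, and any evaluable AH value settles the window. This stands. It limits the point but supplies no rule for those who remain.

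**The SAP's meaning is fairly clear.** SAP 11.3.6.5 and 11.3.6.6 use the same phrase to mean that missing data are not imputed. With 7.6.1.1, the natural reading is available cases plus the rule-based non-responders. This largely stands. A reader might infer that the choice of denominator alone leaves the primary rate open by 4 to 9 points. The documents do not support that: those figures are the distance to a missing = non-responder reading, which no SAP text adopts, at an assumed missing rate. A reader might also infer that the first 11.2.3 analysis cannot be run. It can, on women with observed MBL, but the text does not say so.

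**A rationale may exist elsewhere.** The synopsis ties missing-data handling to the Pivotal Studies, whose documents are not available here, and SAP version 1.0 is not available either. That is possible, but the SAP does not invoke them.

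**Restoring imputation is not the only remedy.** A documented departure with imputation as a sensitivity analysis would also close the gap. The protocol's method, MCMC followed by linear regression, needs care with a volume that has many assigned zeros, and Month 6 largely overlaps the Final Month for completers. The protocol only summarises the percentage, so a pooled CI goes beyond its text. All of this stands and is reflected in the fix.

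**Conclusion.** The concern holds. The SAP departs from the protocol's primary analysis without giving a reason, does not state the denominator, and omits the missing-MBL sensitivity analysis that protocol 8.1.7.1.4 promises. This rests on the text alone and needs no assumption.

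The size does rest on assumptions. With 10% missing and the Phase 2b rates, the as-observed rate would differ from the full-set rate by +7.9 to -2.1 points at 79% and by +9.2 to -0.8 points at 91.9%. The extremes require every missing woman to be a non-responder or every one a responder.

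A reader might infer that the as-observed rate flatters the drug. The documents do not establish that. Some women with missing values bled; others may not have bled, or had unevaluable assays. Response among them is unknown, and the sign depends on it.

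**What to change.** In SAP 11.2.2, restore the protocol's multiple imputation as the primary analysis:

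- state the imputation model and M, allowing for the many assigned zeros and for the overlap of Month 6 with the Final Month;
- set the three discontinuation reasons to non-responder in every imputed dataset;
- put every woman in the full analysis set in her group's denominator;
- give a CI that reflects imputation, for example by Rubin's rules.

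If the sponsor keeps as-observed as primary, document the departure from the protocol, state the denominator, and run the protocol's multiple imputation as a sensitivity analysis.

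In either case:

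- add to 11.2.3 at least one analysis that varies missing-MBL handling, such as missing = non-responder;
- state how women with no observed MBL are handled in the first 11.2.3 analysis;
- report per group the number with missing Final Month MBL and the reason (bled but no products, UBQ not covering the window, unevaluable assay, no UBQ).

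The cost is SAP wording and modest programming with a method the protocol already specifies. No new data are needed. The primary rate may move in either direction.

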key bleeding assessments, specific non-bleeding assessments based on a Non-Bleeding Symptoms Uterine Fibroid Questionnaire (NBUFSQ), and other QOL variables including UFS-QOL. The safety and tolerability objectives include the assessment of standard safety parameters, in addition to hypoestrogenic adverse events of interest, including BMD loss as assessed by dual energy x-ray absorptiometry (DXA) and vasomotor symptoms, such as hot flush. Endometrial health via transvaginal ultrasound (TVU) and endometrial biopsy are also evaluated.

Preliminary results from Cohort 1 demonstrated that treatment with elagolix 300 mg BID plus E2/NETA showed the following:

- Robust efficacy in controlling HMB (composite bleeding endpoint of 91.9%, 85.5%, and 79% in the elagolix 300 mg BID alone, elagolix 300 mg BID plus low-dose E2/NETA, and elagolix 300 mg BID plus standard-dose E2/NETA treatment groups, respectively) associated with uterine fibroids
- Clinically meaningful improvement in quality of life measures and symptom severity scores as assessed by UFS-QOL
- Mitigation of BMD loss at the lumbar spine, with standard-dose E2/NETA
- Substantial dose-dependent reduction in the incidence of vasomotor symptoms, e.g., hot flushes
- No evidence of endometrial safety concerns
- Overall safety profile remains unchanged, with no new or unexpected findings to date.

Overall, preliminary findings from the Phase 2b study suggest that standard-dose E2/NETA as add-back therapy may be effective in preventing BMD loss during treatment with elagolix 300 mg BID, with minimal impact on primary efficacy bleeding endpoints in premenopausal women with HMB associated with uterine fibroids. This dosing regimen could potentially meet the objective of a long-term therapy for the management of symptomatic uterine fibroids in premenopausal women.

Preliminary results from Study M12-813 show that all treatment arms (both doses of elagolix [300 mg BID and 600 mg QD] alone or in combination with either strength of E2/NETA) met the primary endpoint, which is the proportion of subjects who achieved an MBL volume of < 80 mL at the Final Month **and** 50% or greater reduction in MBL volume from Baseline to the Final Month compared to that of placebo (all P < 0.001), as measured by the alkaline hematin method.

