4.3 Sample Size

The two pivotal Studies M12-815 and M12-817 have a planned enrollment of a total of 800 subjects. Based on assumptions related to discontinuation in the pivotal studies and the estimated roll over rate into this extension study, approximately 400 subjects are expected to be enrolled in this extension study.

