11.3.1 Reduction of Bleeding

The change and percent change from Baseline to the observed Final Month in MBL volume will be summarized by analysis group.

The change and percent change from Baseline to each 28-day window starting at Study Day 1 up to Study Day 168 in observed MBL volume in the Treatment Period (i.e., Month 1 (Study Days 1 - 28), Month 2 (Study Days 29 - 56), Month 3 (Study Days 57 - 84), Month 4 (Study Days 85 - 112), Month 5 (Study Days 113 - 140), and Month 6 (Study Days 141 - 168)) will be summarized by analysis group. For observed MBL volume in each 28-day interval, only subjects who did not prematurely discontinue in or before this 28-day interval will be included. For example, for Study Days 29 - 56, it includes subjects who were on treatment for at least 56 days.

Each of the two response criteria that are components of the primary endpoint, i.e., (1) MBL volume of < 80 mL at the Final Month; and (2) 50% or greater reduction in MBL volume from Baseline to the Final Month will be summarized separately in the same way as for the primary analysis. The number and percentage of subjects meeting each criterion at the Final Month will be summarized by analysis group.

The number and percentage of subjects meeting each criterion at the Final Month will also be analyzed in the same way as in each sensitivity analysis for the primary endpoint, and in the analysis for subjects identified in the adenomyosis subset of interest.

The number and percentage of subjects satisfying either (1) MBL volume < 80 mL, or (2) 50% or greater reduction in MBL volume from Baseline, or both will be summarized for every 28-day interval by analysis group based on observed MBL volume.

Plots will be provided by analysis group using the observed MBL volume data:

- Cumulative distribution function for MBL volume at Final Month;
- Cumulative distribution function for percent change from Baseline to Final Month in MBL volume;
- Proportion of responders at Final Month;
- Cumulative distribution function for change from baseline to Final Month in MBL volume.
- Cumulative distribution function for change from baseline in MBL volume to each month;
- Mean change in MBL volume over time.

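### The normal-approximation 95% CI for the primary responder proportion does not reliably reach 95% coverage, chiefly at rates near 92%; a Wilson interval is a better choice

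*SAP*

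**What the plan says.** SAP 11.2.2 reports the number and proportion of responders in each analysis group, and adds: "The 95% CI using the normal approximation to the binomial distribution will also be provided for the proportion of responders in each analysis group". It gives no continuity correction, no exact alternative, and no rule for limits that pass 100%. Protocol 8.1.7.1.1 asks only for the percentage by group, so the interval method comes from the SAP alone.

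The method spreads. SAP 11.2.3 repeats the primary analysis twice. SAP 11.3.1 says that the two component criteria "will be summarized separately in the same way as for the primary analysis".

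SAP 11.1 rules out efficacy tests and states that "summaries in efficacy analysis will be provided by the four main groups as in Section 5.3". On size, SAP 4.3 gives only a total: "approximately 400 subjects are expected to be enrolled in this extension study". Neither document gives the size of any of the four groups, an expected responder rate for this study, or a target interval width.

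The only responder rates in the documents for these regimens are in the Phase 2 efficacy summary of protocol 3.2.2: "composite bleeding endpoint of 91.9%, 85.5%, and 79% in the elagolix 300 mg BID alone", low-dose add-back and standard-dose add-back arms respectively. The first and third of those regimens are studied here.

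**The concern.** The normal-approximation (Wald) interval is centred on the observed proportion and takes its width from that proportion. When the true rate is high and the group is modest, samples with few non-responders give intervals that are too short and sit too high. Actual coverage then falls below 95%, and most of the misses have the lower limit above the true rate. Upper limits above 100% also become possible.

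At stake is the answer to one question: how low could the long-term responder rate plausibly be? With no planned comparison, that answer comes from the lower limit of this interval, and the error runs in the favourable direction.

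**Working it through.** **The plan's own figure.** The only sample-size figure is about 400 enrolled from 800 in the pivotal studies: 400/800 = 50%. It cannot be reproduced further, because the discontinuation and rollover assumptions are not given. There is no precision figure to reproduce.

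**Inputs.**
- Method: two-sided 95% Wald interval (SAP 11.2.2), z = 1.96.
- True rates: 79% and 91.9% (protocol 3.2.2, preliminary Phase 2b results), and the range 79-92%.
- Group sizes (assumption): former placebo women are 25% to 33% of 400 and are split 1:1. That gives 400 × 0.25 / 2 = 50 to 400 × 0.333 / 2 ≈ 67 per re-randomised group. Equal pivotal allocation would put about 400/3 ≈ 133 in each continuing group; a 1:1:2 allocation would put 100 and 200. The pivotal ratio is not in the documents.

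**Formulas**, with x responders out of n and p̂ = x/n.
- Wald: p̂ ± 1.96 √[p̂(1 − p̂)/n].
- Wilson: [p̂ + z²/(2n) ± z √(p̂(1 − p̂)/n + z²/(4n²))] / (1 + z²/n).
- Exact coverage at true rate p: the sum of the Binomial(n, p) probabilities of every x whose interval contains p.

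**One case in full: n=50, p=91.9%.**
- The lower limit exceeds 91.9% when x=49 (94.1%) or x=50 (interval 100% to 100%). Probability: 0.0646 + 0.0146 = 0.079.
- The upper limit falls below 91.9% when x ≤ 40 (91.1% at x=40). Probability: 0.006.
- Coverage: 1 − 0.079 − 0.006 = 0.915.
- The upper limit exceeds 100% when x = 47, 48 or 49. Probability: 0.197 + 0.139 + 0.065 ≈ 0.40.

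**At single rates.**

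| n | Wald coverage, 91.9% | Lower limit above truth, 91.9% (nominal 2.5%) | Upper limit > 100%, 91.9% | Wilson coverage, 91.9% | Wald coverage, 79% |
|---|---|---|---|---|---|
| 50 | 91.5% | 7.9% | 40% | 93.9% | 95.6% |
| 67 | 90.9% | 8.4% | 19% | 93.3% | 94.3% |
| 100 | 90.9% | 8.5% | 3.4% | 95.9% | 92.8% |
| 133 | 90.9% | 8.0% | 0.45% | 94.5% | 95.3% |
| 200 | 92.6% | 6.3% | <0.01% | 94.9% | 95.2% |

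At 79% the chance of an upper limit above 100% is 0.4% at n=50, 0.01% at n=67, and practically nil beyond.

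**Averaged over true rates 79-92% (minimum in brackets).**

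| n | Wald | Wilson | Clopper-Pearson |
|---|---|---|---|
| 50 | 92.2% (85.7%) | 95.2% (93.1%) | 97.0% (95.3%) |
| 67 | 92.8% (87.8%) | 95.1% (93.0%) | 96.7% (95.2%) |

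**What a report would show.** For 46/50, Wald gives 84.5-99.5% and Wilson 81.2-96.8%. For 48/50, Wald gives 90.6-101.4% and Wilson 86.5-98.9%. For 40/50, Wald gives 68.9-91.1% and Wilson 67.0-88.8%.

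**The case against.** The strongest reply is that little depends on the interval. Efficacy is descriptive (SAP 11.1 and 11.4), with no threshold, comparison or sample size tied to these limits. Responder counts are reported, so any reader can compute another interval. All of that stands, and it is why severity is low. It does not excuse an interval labelled 95% that covers about 91% near one regimen's Phase 2b rate.

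A second reply is that the shortfall is concentrated in elagolix alone, which the protocol treats as a reference arm. The regimen the programme aims to support, with standard-dose add-back, had a Phase 2b rate of 79%, where coverage is close to nominal at most sizes. This stands too, with an exception at n=100 (92.8%).

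Several stronger readings are tempting, and the documents do not support them:
- That the plan's precision figure is wrong. It states none.
- That rates of 79-92% are expected in this study. They are Phase 2b background results.
- That the interval under-covers at every such rate and size. At 79% and n=50 it covers 95.6%.
- That coverage falls below 85%. At n=50 or 67 that requires true rates above 92%, beyond the Phase 2b rates.
- That the adenomyosis subset is affected. SAP 11.2.4 plans only a summary of the proportion there and no interval.

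Wilson is not perfect either: at 91.9% it covers 93.9% at n=50 and 93.3% at n=67. Its misses there lean the other way, with the upper limit below the truth.

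**Conclusion.** The concern holds as a low-severity point about method. At the Phase 2b rates for the two study regimens, the interval named in SAP 11.2.2 does not reliably reach its nominal level. In groups of 50 to 67 the average loss over 79-92% is about 2 to 3 percentage points. At 91.9% coverage is about 91% for every size from 50 to 133 and 92.6% at 200, so the finding at that rate does not hinge on the assumed allocation. What does depend on group size is the chance of an upper limit above 100%, which is material only in the smaller groups. The conclusion assumes that true rates here lie near those seen in Phase 2b. Point estimates do not change.

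**What to change.** In SAP 11.2.2, replace the normal approximation with the Wilson score interval for the responder proportion in each analysis group. Clopper-Pearson is an acceptable alternative if guaranteed coverage is preferred, at the price of being conservative (average 97.0% at n=50). Apply the same method to the sensitivity analyses in 11.2.3 and the component criteria in 11.3.1, so that the intervals can be compared.

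The cost is one sentence in the SAP and a changed programming option; no new data or protocol amendment is needed. Lower limits become slightly less favourable: 84.5% to 81.2% for 46/50, and 68.9% to 67.0% for 40/50.
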